10.2.1 Primary efficacy variable

Baseline and Month 6 modified BPI-SF3 scores will be obtained by averaging the weekly modified BPI-SF3 scores over the 4 weeks prior to the corresponding visit of interest (randomization visit and Month 6 visit, respectively). At least 4 of the 7 daily scores should be non-missing to derive a valid weekly modified BPI-SF3 score and at least 3 valid weekly scores should be non-missing to derive a valid score for the relevant time period.

All available daily scores will be used to derive the scores regardless of study treatment discontinuations or introductions of new medications.

In addition, intermediate monthly modified BPI-SF3 scores from Month 1 to Month 5 will be derived with the same validity conditions. The selection of daily scores over 4 weeks for these time points will be described in the SAP.

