### 3.4 Efficacy estimands

The estimands targeted by the primary and secondary efficacy objectives and analyses are defined in [Table 1](#).

A treatment policy strategy will be applied for all estimands defined in [Table 1](#), i.e., all collected endpoint data are used in the analyses regardless of occurrence of any intercurrent events (ICEs). Expected ICEs are premature treatment discontinuation as well as use of other medications.

Fabry disease medications (e.g., ERT) are forbidden by the protocol as they are not part of the treatment condition of interest [see definition in [Table 1](#)]. However, considering that forbidden medications could be taken in clinical practice, data collected during use of forbidden medications will be included in the analyses.

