**Table 4 Daily scores used for derivation of monthly scores**

Monthly score	First study day	Last study day
Baseline	-28	-1
Month 1	3	30
Month 2	34	61
Month 3	64	91
Month 4	95	122
Month 5	125	152
Month 6	Month 6 visit* – 28 days	Month 6 visit* – 1 day

\* If Month 6 visit is on Day 198 or later (i.e., out of protocol defined visit window), use Day 169 to 196 instead. If Month 6 visit is on Day 168 or earlier (i.e., out of protocol defined visit window), the Month 6 score will be missing.

It may be noted that for subjects with a Month 6 visit performed earlier than Day 181, there will be an overlap between the 28 days used to derive the Month 5 monthly score and the 28 days used to derive the Month 6 monthly score.

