### 9.2.1 Change from baseline to Month 6 in the NRS-11 score of “abdominal pain at its worst in the last 24 hours” in subjects with GI symptoms at baseline

Using the abdominal pain intensity scores collected daily, the variable change from baseline to Month 6 in the NRS-11 score of “abdominal pain at its worst in the last 24 hours” will be derived using the same rules as those described for the primary efficacy variable [see Section 9.1].

The variable will be derived for all subjects and displayed in data listings but used only on mFAS-GIS.

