**Table 5 Time windows for visit re-mapping**

Visit	Study day (nominal value)	Lower limit study day	Upper limit study day
Baseline	1	Day of screening visit	1
Month 1	30	2	45
Month 2	61	46	75
Month 3	91	76	106
Month 4	122	107	136
Month 5	152	137	167
Month 6	183	168	213

Should more than one value fall within the same time window, then the closest value to the planned study day will be assigned to the visit. If the values are equidistant to the planned study day, the latest value will be retained.

Using the plasma Gb3 data collected at baseline and Month 6, the change from baseline to Month 6 will be calculated as the difference (Month 6 – baseline) and also as the percent change from baseline ( $100 \times [\text{Month 6} - \text{baseline}] / \text{baseline}$ ).

Values reported as below the limit of quantification (BLQ) will be set to the limit of quantification in the analyses. The number of values reported as BLQ by treatment group and visit will be included in the tables.

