### 15.2.3 Primary statistical analysis

The primary analysis will be performed on the mFAS, according to the intent-to-treat approach. All available data will be used regardless of occurrences of ICEs, such as premature treatment discontinuation or changes in background medication.

The null hypothesis will be tested using the two-sided significance alpha level = 0.05, using the following method.

The observed data cannot be used to distinguish between missing at random (MAR) and missing not at random (MNAR) missing data mechanisms [NRC Report 2010] and in incomplete-data settings a definitive MNAR analysis does not exist [Molenberghs 2004].

An analysis based on a pattern-mixture model will be performed using a MAR imputation in the placebo arm while using a MNAR approach in the lucerastat arm: missing data will be imputed applying a control-based multiple imputation (MI) assuming MNAR using the CR approach [Carpenter 2013]. Instead of imputing a single value for each missing observation, a set of values is generated from the model, resulting in as many distinct complete datasets without missing data. The imputation model includes the baseline value, the two stratification factors (sex and ERT treatment status at screening) and all post-baseline monthly scores up to Month 6. Missing data for subjects from both treatment arms will be imputed using data from the placebo arm. This approach assumes that subjects with missing data in the lucerastat arm have outcomes trending towards outcomes observed in the placebo arm, i.e., the imputations result in a treatment effect that gradually diminishes towards the placebo arm.

More specifically, the imputations will be performed in two steps: “intermittent” missing data (a monthly score is missing but one or more monthly score[s] is [are] available in following month[s]) will be first imputed by a Markov chain Monte Carlo method using a non-informative Jeffreys prior, thus creating 500 partially imputed “monotone” datasets; then, the remaining missing data will be imputed once in each of these 500 “monotone” imputed datasets using the CR approach leading finally to 500 complete imputed datasets. Imputed values will be restricted to remain in the clinically relevant range of [0, 10].

The two-step MI procedure will be implemented by the following SAS® code:

```

proc mi data=h nimpute=500 seed=32767 minimum = . . . . 0 0 0 0 0 0 maximum = . . . . 10
10 10 10 10 10 minmaxiter= 1000000out=h2;

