### 15.2.5.1 Responder analysis

A cut-off of 30% in pain reduction was selected for this responder analysis because this 30% reduction in pain has been shown to represent important improvement in patients with neuropathic pain [Farrar 2001] and it is recommended that the percentages of patients responding with this degree of pain relief be reported in clinical trials of chronic pain treatments [Dworkin 2008]. Based on the evidence found in the literature in non-Fabry patients with neuropathic pain and regulatory guidelines [EMA 2007] (later replaced by [EMA 2017]), a cut-off of 30% was selected.

Using subject responses from the modified BPI-SF3, a response variable (yes/no) for the primary endpoint will be calculated based on a reduction of at least 30% from baseline to Month 6 in the modified BPI-SF3 score of “neuropathic pain at its worst in the last 24 hours”.

Subjects who have a missing modified BPI-SF3 score at Month 6, for any reason, will be considered as non-responders, i.e., the worst possible outcome is assumed.

The Cochran-Mantel-Haenszel (CMH) test stratified by sex and ERT treatment status at screening (treated vs not treated) will be used to test for a difference in the proportions of responders at Month 6 between treatment groups.

The treatment effect (lucerastat vs placebo) will be expressed in terms of the common odds ratio (ORc) and corresponding 95% CI. An  $ORc > 1$  will indicate a response to treatment in favor of lucerastat as compared to placebo.

Homogeneity of the treatment effect across strata will be investigated using the Breslow-Day test.

This analysis will be implemented by the following SAS® code:

```
proc freq;
  tables sex*ertstatus*treatment*response / nocol nopercnt cmhl
  commonriskdiff (cl=newcombe);
run;
```

The Mantel-Haenszel risk (proportion) difference (lucerastat vs placebo) and corresponding 95% CI (stratified by sex and ERT treatment status at screening) will also be provided. The CIs are calculated using the stratified Newcombe method [Yan 2010].

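### SAP Table 4 sets the Month 6 pain score to missing for every Month 6 visit on Day 168 or earlier, even when the diary meets the protocol's validity rule, while late visits are still scored

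*SAP*

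**What the plan says.** Protocol 10.2.1 and SAP 9.1 build the Month 6 modified BPI-SF3 score from weekly averages over the four weeks before the Month 6 visit. The validity rule is: "At least 4 of the 7 daily scores should be non-missing to derive a valid weekly modified BPI-SF3 score", with at least three valid weeks. Neither section adds a condition on the day of the visit. For the choice of days, Protocol 10.2.1 refers to the SAP only for Months 1 to 5.

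The footnote to SAP Table 4 then treats the two kinds of out-of-window visit differently:

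- Late: "If Month 6 visit is on Day 198 or later (i.e., out of protocol defined visit window), use Day 169 to 196 instead".
- Early: "If Month 6 visit is on Day 168 or earlier (i.e., out of protocol defined visit window), the Month 6 score will be missing".

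Protocol Table 5 gives the visit window as Day 169 to Day 197. SAP 15.2.2 says that everything collected up to the Month 6 visit goes into the primary analysis. SAP section 20, which records departures from the protocol's analyses, covers subgroups only.

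A missing Month 6 score is handled in SAP 15.2.3 by Copy Reference: "Missing data for subjects from both treatment arms will be imputed using data from the placebo arm". In SAP 15.2.5.1: "Subjects who have a missing modified BPI-SF3 score at Month 6, for any reason, will be considered as non-responders". For abdominal pain, SAP 9.2.1 says that the variable "will be derived using the same rules as those described for the primary efficacy variable". SAP 9.2.2 gives diarrhea its own rule of at least 21 measures and does not say whether the Table 4 footnote applies.

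**The concern.** Both out-of-window cases carry the same stated reason, yet one is rescued and the other is discarded whatever the diary holds. A subject who comes one day early, with a diary that is complete up to the visit, loses the primary endpoint value. A subject who comes weeks late keeps it.

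What is at stake is observed primary-endpoint data. For a lucerastat subject the observed score is replaced by a draw from a placebo-based model. Months 1 to 5 still inform that draw, so the effect is diluted rather than erased. In every responder analysis the subject becomes a non-responder. The third endpoint in the testing sequence, abdominal pain, is affected in the same way.

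**Working it through.** **1. The plan's own power figure.** Inputs from Protocol 10.5: difference 2, SD 3, two-sided 5%, 66 versus 33. The noncentrality is 2 / (3 × √(1/66 + 1/33)) with 97 degrees of freedom. The two-sample t-test power is 87.2%, which matches the protocol. With the 118 subjects in SAP section 2 (about 79 versus 39) it is 92.2%.

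**2. Windows around the cut-off.**

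| Month 6 visit | Four weeks before visit | SAP Table 4 |
|---|---|---|
| Day 168 | Days 140–167 | missing |
| Day 169 | Days 141–168 | scored, Days 141–168 |
| Day 197 | Days 169–196 | scored, Days 169–196 |
| Day 198 | Days 170–197 | scored, Days 169–196 |
| Day 210 | Days 182–209 | scored, Days 169–196 |

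The late rule borrows the window of the last allowed visit. The counterpart for early visits would be the window of the first allowed visit, Days 141–168.

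**3. Which early visits could be scored on Days 141–168?** Assume consecutive weeks (141–147, 148–154, 155–161, 162–168) and a complete diary ending the day before the visit. A week counts if it has at least 4 days, and at least 3 weeks are needed.

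| Visit | Days per week | Valid weeks | Mean day of score | Ratio to 168.5 |
|---|---|---|---|---|
| 158 | 7, 7, 3, 0 | 2 | missing | – |
| 159 | 7, 7, 4, 0 | 3 | 150.5 | 0.893 |
| 162 | 7, 7, 7, 0 | 3 | 151.0 | 0.896 |
| 165 | 7, 7, 7, 3 | 3 | 151.0 | 0.896 |
| 166 | 7, 7, 7, 4 | 4 | 154.1 | 0.915 |
| 168 | 7, 7, 7, 6 | 4 | 154.4 | 0.916 |
| 169 | 7, 7, 7, 7 | 4 | 154.5 | 0.917 |

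The reference 168.5 is the centre of Days 155–182, the window of a visit on the nominal Day 183. The ratio is the share of the effect kept if benefit builds up linearly, which is an assumption. Day 162 is the first visit day with three complete weeks. Days 141–152 (12 days) also belong to Month 5, exactly as they do for the accepted Day 169 visit.

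**4. Illustrative size.** Let *m* be the share of subjects with an early visit and *r* the share of the effect that the substitute value keeps. Both are assumptions. The diluted difference is 2 × (1 − *m*(1 − *r*)). For example, *m* = 5% and *r* = 0 gives 2 × 0.95 = 1.90. Power at 79 versus 39:

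| *m* | Current rule, *r* = 0 to 0.8 | Scored on Days 141–168, *r* = 0.896 to 0.916 |
|---|---|---|
| 2% | 91.2% to 92.0% | 92.1% |
| 5% | 89.4% to 91.7% | 91.9% to 92.0% |
| 10% | 86.0% to 91.2% | 91.7% to 91.8% |

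The right-hand column assumes that all early visits fall on Days 162–168. The formula leaves the SD unchanged and ignores imputation variance and the extra noise of shorter windows.

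**The case against.** The best case for the footnote is that Protocol 10.2.1 anchors the score on the Month 6 visit, whose window starts at Day 169, so that an earlier visit is not a Month 6 visit at all. Visit 8 doubles as the end-of-treatment visit and the last PTOP visit doubles as the end of PTOP, so a day cut-off keeps early leavers out cleanly. Early and late visits also differ in kind: the diary is handed back at the last visit, so part of Days 141–168 cannot be observed for an early visit, whereas Days 169–196 have already passed for a late one. These points stand, and they shape the fix. They do not justify discarding a diary that meets the validity rule, because early leavers can be excluded by name.

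Table 4 also leaves some diary days unused for accepted visits: a Day 197 visit leaves Days 153–168 (16 days) in no monthly score. SAP 15.2.2 therefore cannot mean every single day. The difference is that the Day 197 subject still has an observed Month 6 score. The MAR and MMRM analyses are useful checks, but they start from the same missing score.

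Some stronger readings are not supported:

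- A reader might cite SAP 3.4, "all collected endpoint data are used in the analyses regardless of occurrence of any intercurrent events". That sentence concerns intercurrent events such as stopping treatment or taking other medication. A mistimed visit is neither.
- A reader might infer that the rule favours lucerastat. It applies to both arms alike, and placebo-based imputation dilutes the effect.
- A reader might infer that the rule removes everyone who stops treatment early. Those subjects are followed to a Month 6 PTOP visit.
- A reader might infer a material loss of power. No count of early visits is given.

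**Conclusion.** The point holds as an inconsistency that is cheap to repair. The SAP adds an unconditional visit-day condition that Protocol 10.2.1 does not contain, that sits against SAP 15.2.2 and that section 20 does not declare. Its effect is to replace valid observed scores with placebo-based imputations or non-response.

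The size is unknown. It is nil if nobody attended on Day 168 or earlier, and small for a handful of subjects. The power figures rest on assumed shares of early visits, an assumed range for what imputation preserves and an assumed linear build-up of effect. They show an order of magnitude and are not a forecast. The primary analysis is not invalidated.

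**What to change.** Replace the early-visit sentence in the Table 4 footnote with:

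> If the scheduled Month 6 visit, or the Month 6 PTOP visit, is on Day 162 to 168, use Day 141 to 168 under the existing validity rule. EOT visits held for premature discontinuation and End-of-PTOP visits held because of early withdrawal do not count as Month 6 visits. For a Month 6 visit on Day 161 or earlier the score is missing.

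Day 162 is proposed because three complete diary weeks can exist from then on, and because it lies outside the protocol's Month 5 visit window (Day 145 to 159). List the Month 6 windowing rule, early and late, in section 20. State in 9.2.2 whether it applies to diarrhea; with a complete diary, the 21-measure rule would be met for visits on Days 162 to 168.

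The cost is one footnote rule, one line in each of two sections and a few lines of derivation code, all before the blind is broken. There are two downsides. Affected subjects have 21 to 27 somewhat earlier diary days, up to 12 of them shared with Month 5; under linear build-up the shortfall is 8.4% to 10.4%, against 8.3% already accepted for a Day 169 visit. SAP Table 5 ("Time windows for visit re-mapping") opens Month 6 at Day 168, so it now disagrees with Table 4 on that one day. The change removes that disagreement, but visits on Days 162 to 167 would then give a Month 6 pain score while plasma Gb3 and the site-visit questionnaires map to Month 5. Those subjects have no Month 6 value from that visit for either today, so nothing is lost.

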## 9.2 Secondary efficacy endpoints

As outlined in protocol section 10.2.2, the following 3 secondary efficacy endpoint variables are considered:

- Change from baseline to Month 6 in the NRS-11 score of “abdominal pain at its worst in the last 24 hours” in subjects with GI symptoms at baseline;
- Change from baseline to Month 6 in the number of days with at least 1 stool of a BSS consistency Type 6 or 7 in subjects with GI symptoms at baseline;
- Change from baseline to Month 6 in plasma Gb3.

### 9.2.1 Change from baseline to Month 6 in the NRS-11 score of “abdominal pain at its worst in the last 24 hours” in subjects with GI symptoms at baseline

Using the abdominal pain intensity scores collected daily, the variable change from baseline to Month 6 in the NRS-11 score of “abdominal pain at its worst in the last 24 hours” will be derived using the same rules as those described for the primary efficacy variable [see Section 9.1].

The variable will be derived for all subjects and displayed in data listings but used only on mFAS-GIS.

### 9.2.2 Change from baseline to Month 6 in the number of days with at least 1 stool of a BSS consistency Type 6 or 7 in subjects with GI symptoms at baseline

Using the number of bowel movements with BSS consistency of Type 6 or 7 collected daily, the variable “change from baseline to Month 6 in the number of days with at least one stool of a BSS consistency Type 6 or 7” (i.e., “number of days with diarrhea”) will be derived using the following rules:

- The number of days with diarrhea at baseline and Month 6 will be calculated as the number of days observed with diarrhea over the 4 weeks prior to the corresponding visit of interest (randomization and Month 6, respectively) over the number of days with data available multiplied by 28, provided there are at least 21 measures available in the corresponding time period.

The variable will be derived for all subjects and displayed in data listings but used only on mFAS-GIS. All available data will be used to derive the number of days with diarrhea regardless of study treatment discontinuations. In addition, the intermediate number of days with diarrhea from Month 1 to Month 5 will be derived in the same way.

### 9.2.3 Change from baseline to Month 6 in plasma Gb3 (ng/mL)

Plasma Gb3 data will not be available for statistical analysis until the study database is locked and the randomization code is broken.

The values collected during the study will be mapped to protocol visits according to the windowed times described in [Table 5](#).

**Table 5 Time windows for visit re-mapping**

Visit	Study day (nominal value)	Lower limit study day	Upper limit study day
Baseline	1	Day of screening visit	1
Month 1	30	2	45
Month 2	61	46	75
Month 3	91	76	106
Month 4	122	107	136
Month 5	152	137	167
Month 6	183	168	213

Should more than one value fall within the same time window, then the closest value to the planned study day will be assigned to the visit. If the values are equidistant to the planned study day, the latest value will be retained.

Using the plasma Gb3 data collected at baseline and Month 6, the change from baseline to Month 6 will be calculated as the difference (Month 6 – baseline) and also as the percent change from baseline ( $100 \times [\text{Month 6} - \text{baseline}] / \text{baseline}$ ).

Values reported as below the limit of quantification (BLQ) will be set to the limit of quantification in the analyses. The number of values reported as BLQ by treatment group and visit will be included in the tables.

### 9.3 Renal function endpoints

#### 9.3.1 Subject eGFR slope from baseline to Month 6

Using all eGFR values from baseline to Month 6, the subject eGFR slope (mL/min/1.73 m^2 per year) will be estimated via a linear mixed model, as described in Section 15.4.1.1.

#### 9.3.2 Change from baseline to Month 6 in UACR

UACR will be derived by dividing urine albumin by urine creatinine. Urine albumin values reported as BLQ will be set to the limit of quantification and values reported as > x.x (above x.x) will be set to x.x (equal to x.x) before deriving UACR.

The values collected during the study will be mapped to protocol visits according to the windowed times described in Table 5.

### 9.4 Echocardiography-based endpoints

The echocardiography variables are listed in Table 6.

**Table 6 Echocardiography variables**

Variable	Test name in SDTM data
LVM indexed to Height (g/m 2.7 )	Left Ventricular Mass Height 2.7 (LVMH)
LVM indexed to BSA (g/m  )	Left Ventricular Mass Index (LVMASIDX)*
Left Ventricular Posterior Wall Thickness (mm)	Posterior Wall Thickness - End Diastole (LVPWD)
Left Ventricular Interventricular Septum Thickness (mm)	Cross-sec Thickness, EVD (THCKEVD)
Left Ventricular Mean Wall Thickness (mm)	Mean Wall Thickness (LVMWT2D)
LVEF (%)	Left Ventricular Ejection Fraction (LVEF)
Left Ventricular End Diastolic Volume indexed to BSA (mL/m  )	Left Ventricle End Diastolic Volume BP (EDVB)*
Left Ventricular End Systolic Volume indexed to BSA (mL/m  )	Left Ventricle End Systolic Volume BP (ESVB)*
Left Atrial Volume indexed to BSA (mL/m  )	Left Atrium - End Systolic Volume BP (LAB)*

\* Variables provided by vendor are not indexed to BSA and will therefore be indexed to BSA as described below.

BSA will be derived using the Mosteller formula:

$$BSA(m^2) = \sqrt{\frac{\text{height (cm)} * \text{weight (kg)}}{3600}}$$

Height at screening will be used. The last available weight measurement collected up to or on the date of the respective echocardiography assessment will be used. Variables will be indexed to BSA by dividing the measurement by BSA, if applicable [see [Table 6](#)].

The values collected during the study will be mapped to protocol visits according to the windowed times described in [Table 5](#), with the exception that the upper limit study day for baseline will be Day 14, i.e., re-tests occurring within 14 days (included) after the randomization visit, will also be considered as baseline value for the echocardiography endpoints, if no value on or prior to Day 1 is available. Re-tests are performed if the original assessment from randomization is not evaluable or declined by the independent central reader as being of poor quality. Using these re-test assessments as baseline value is acceptable because no changes in echocardiography endpoints are expected in such a short period of 14 days.

For each echocardiography-based endpoint, absolute values and changes from baseline to Month 6 (expressed as difference and expressed as percent change) will be summarized by treatment group and visit.

The change from baseline to Month 6 of each parameter will be calculated as the difference (Month 6 – baseline). In addition, the percent change from baseline to Month 6 will be calculated as  $100 \times (\text{Month 6} - \text{baseline}) / \text{baseline}$ .

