6.1.4.2 Echocardiography-based endpoints

- Change from baseline to Month 6 in LVMI, posterior wall thickness, left ventricular mean wall thickness, left ventricular ejection fraction (LVEF), left ventricular end diastolic and end systolic volumes, left atrial volume, as measured by echocardiography.

Of note, long-term outcome of lucerastat on echocardiography parameters will be further assessed in the OLE study (separate protocol).

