7.2.2.7 Echocardiography

A central echocardiography vendor (see echocardiography manual for contact details) will be used for all protocol-mandated echocardiographies, including re-tests, and echocardiographies performed at unscheduled visits.

A re-test may be performed if the result for an echocardiography is missing (e.g., unreadable echocardiography) or to repeat an abnormal echocardiography. A re-test does not need to be reported as an unscheduled visit [see Section 7.1.2].

Standard 2D/Doppler echocardiographies will be collected at the randomization visit, and Month 6 (Month 6 PTOF visit if subject is in the PTOF). Echocardiographies will be acquired by trained sonographers/technicians using the echocardiography Image Acquisition Guidelines. The sonographers/technicians will have to be qualified by the central echocardiography vendor prior to any acquisition of echocardiographies in a study subject. Whenever possible, the same sonographer/technician should acquire all echocardiographies performed in one subject. The site personnel will electronically transmit the echocardiographies to the central echocardiography vendor for central reading.

The overview of the assessment criteria and read procedures used by the echocardiography vendor will be described in a charter.

Central echocardiography reports will be provided by the central echocardiography vendor to the investigator/delegate. In the event of specific echocardiography abnormalities, the central echocardiography vendor will alert the sponsor and the site personnel. All

echocardiography reports must be reviewed, signed, and dated by the investigator/delegate within 10 working days of receipt and filed with the source documentation.

Incidental clinically relevant findings on echocardiographies will be reported in the Medical History or as an AE in the eCRF, as applicable.

The measures/assessments evaluated by the central echocardiography vendor include but are not limited to:

- LVMI for height^{2.7} (g/m^{2.7});
- Posterior wall thickness (mm);
- Left ventricular mean wall thickness (mm);
- LVEF (%);
- Left ventricular end diastolic volume (mL);
- Left ventricular end systolic volume (mL);
- Left atrial volume (mL).

Details on echocardiography procedures (recording, transfer of data and reporting) will be provided in the echocardiography manual.

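### The SAP analyses the three cardiac volumes only after dividing by a BSA that follows weight, so a between-arm difference in weight change would shift the comparison; analyse the volumes in mL as well

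*SAP*

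**What the plan says.** Protocol 6.1.4.2 lists among the other efficacy endpoints the change from baseline to Month 6 in "left ventricular end diastolic and end systolic volumes, left atrial volume, as measured by echocardiography". It states no unit and no indexing for these volumes. Protocol 7.2.2.7 lists what the central vendor evaluates, and the three volumes are there in mL; the first entry begins "Left ventricular end diastolic volume (mL". Only left ventricular mass carries an index in that list ("LVMI for height" to the power 2.7).

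SAP Table 6 has the volumes in one form only, for example "Left Ventricular End Diastolic Volume indexed to BSA" in mL/m². Its footnote explains: "Variables provided by vendor are not indexed to BSA and will therefore be indexed to BSA as described below". The text below the table gives the Mosteller formula, fixes height at screening, and says of weight: "The last available weight measurement collected up to or on the date of the respective echocardiography assessment will be used". Left ventricular mass appears twice, once indexed to height and once to BSA.

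SAP 9.4 summarises values and changes by treatment group. SAP 15.4.2 fits an ANCOVA to the change in each echocardiography parameter, with terms for baseline value, sex, ERT status and treatment, and repeats it on the log scale. Neither section specifies an analysis of the un-indexed volumes or a term for weight. SAP Section 20 contains only subgroup changes.

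**The concern.** An indexed volume is a ratio, and both parts can change over six months. If the denominator is recomputed at Month 6, the change score mixes a change in chamber volume with a change in weight. The model has nothing that separates them, and no companion analysis in mL would let a reader do so.

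The treatment comparison is affected when weight moves differently in the two arms. Indexed volumes would then differ between arms even if every volume in mL stayed the same, and a real volume difference could be partly hidden or enlarged. For left ventricular mass, Table 6 keeps the height-indexed form, which does not use weight. The three volumes have no weight-free counterpart anywhere in the plan.

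**Working it through.** **The plan's own figure.** There is none to reproduce. The documents give no expected change, SD or power for any echocardiography variable, and no expected weight change.

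**Inputs.**
- BSA = √(height in cm × weight in kg / 3600): SAP 9.4, Mosteller.
- Height: screening value at both times (SAP 9.4).
- Weight: most recent value at each echocardiogram (SAP 9.4). Protocol Table 5 schedules weight at both the randomization and Month 6 visits, when echocardiography is done.
- Model terms: SAP 15.4.2, no weight term.
- Weight change w (as a fraction): assumed.

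**Step 1: one subject.** Let V be the volume in mL, W the weight and I = V/BSA. With height fixed,

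I(Month 6)/I(baseline) = [V(Month 6)/V(baseline)] / √[W(Month 6)/W(baseline)].

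If V does not change and weight changes by w, the indexed volume changes by 1/√(1 + w) − 1.

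| Weight change | Change in indexed volume, mL unchanged |
|---|---|
| −5% | 1/√0.95 − 1 = +2.60% |
| −2% | 1/√0.98 − 1 = +1.02% |
| +2% | 1/√1.02 − 1 = −0.99% |
| +5% | 1/√1.05 − 1 = −2.41% |

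Illustration with assumed values of 170 cm, 75 kg and a constant end diastolic volume of 120 mL: baseline BSA is √(170 × 75/3600) = 1.882 m², giving 63.76 mL/m². At 71.25 kg (5% lighter) BSA is 1.834 m², giving 65.42 mL/m². The recorded change is +1.66 mL/m², or +2.6%, with none in mL.

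**Step 2: the treatment comparison.** On the log scale that SAP 15.4.2 also uses,

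change in log I = change in log V − 0.5 × change in log W.

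Taking the difference between arms, and leaving aside the baseline and stratum adjustment:

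treatment difference in log I = treatment difference in log V − 0.5 × treatment difference in log W.

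Only the between-arm difference in weight change enters. If mean log weight falls by the equivalent of 2% on lucerastat relative to placebo, the indexed comparison moves by about +1.0%; for 5%, by +2.6%. Relative weight gain on lucerastat moves it the other way (−0.99% and −2.41%).

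**Step 3: a weight change common to both arms.** If both arms lose 5%, each arm's indexed volume rises by 2.60% and the ratio between arms stays at 1, so the log-scale comparison is untouched. On the original scale each subject's change shifts by 2.60% of the baseline indexed value. With similar baseline means after randomization this also nearly cancels. The within-arm summaries in SAP 9.4 still show a rise.

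**Step 4: which variables.** The three volumes and left ventricular mass per BSA are affected. Height-indexed mass, wall thicknesses, septum thickness and ejection fraction do not use weight.

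**Step 5: effect of the remedy.** In mL, an unchanged volume shows a 0% change whatever the weight does. With baseline BSA at both visits the denominator cancels from the ratio in Step 1, and the percent change again equals that of the volume in mL.

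**The case against.** The strongest reply is that the SAP acted within its authority. A reader might infer that it has replaced an endpoint the protocol defined in mL. The documents do not support that. Protocol 6.1.4.2 gives no unit for the volumes, the mL entries in 7.2.2.7 describe vendor output in a list that is expressly not exhaustive, and Protocol 10.2 and 10.3.4 leave the detailed variables and analyses of other endpoints to the SAP. The protocol set out no specific echocardiography analysis that Section 20 had to record as changed. This stands, and an entry in Section 20 is a matter of transparency. It is still true that the protocol names the volumes un-indexed and the SAP never analyses them that way.

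A reader might also infer that lucerastat is expected to alter weight, since weight is a safety endpoint. The documents list it with the vital signs and give no such reason; the clinical and nonclinical summaries in the protocol report no weight effect. A differential change is conceivable, because the protocol hopes for relief of gastrointestinal symptoms and lists poor weight gain among them, but nothing predicts it. Nor does the 10% limit in SAP Table 19 indicate a plausible difference between arm means: it is a per-subject safety flag.

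Third, concurrent BSA is a legitimate choice. If chamber volume varies with body size, the mL analysis could show a weight effect as a cardiac one. Concurrent and baseline BSA therefore answer different questions, and neither is an error. That argues for reporting the mL volumes beside the indexed ones and against dropping the indexing.

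Finally, SAP 16.3.1 summarises weight change by visit and arm, so a marked imbalance would be visible. That helps only partly. Those summaries use the safety set and stop 30 days after the end of treatment, whereas the echocardiography analysis uses the mFAS and can include post-treatment Month 6 data. They also do not turn a weight difference into its effect on the indexed estimate.

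**Conclusion.** The point holds as a low-priority improvement. As written, the plan cannot distinguish a treatment difference in the three volumes from a treatment difference in weight, because the volumes are analysed only per concurrent BSA and without a weight term. The direction and the factor of about one half follow from the Mosteller formula with fixed height. The size rests on an assumed between-arm difference in weight change: about 1% for a 2% difference and 2.6% for a 5% difference. No expected effect or SD is given against which to judge these figures, so how much they could mask or mimic cannot be stated.

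These are other efficacy endpoints outside the four-hypothesis fixed sequence. The primary and secondary results and the Type I error control are unaffected.

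**What to change.** In SAP Table 6, add left ventricular end diastolic volume, end systolic volume and left atrial volume in mL. In SAP 15.4.2, apply the same ANCOVA to them and report the results next to the BSA-indexed versions, which stay.

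Optionally, add a sensitivity analysis of the BSA-indexed variables, including left ventricular mass per BSA, with baseline BSA at both visits.

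In SAP Section 20, add a sentence saying that the volumes are also presented indexed to BSA, and why.

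The cost is small. The vendor already supplies the un-indexed volumes, so the main addition is three variables on the original and log scales (3 × 2 = 6 model fits). The downside is a few more exploratory results to report.
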